Wounds will be assessed postoperatively at regular intervals until wound healing is achieved. This will occur at least 2 and 6 weeks after surgery, which are standard intervals in our current postoperative protocol. No additional office visits will be needed for patients in the control or treatment arms. Photodocumentation of the wounds will occur at two and six weeks postoperatively. Primary outcome measure will be uneventful wound healing (requiring no intervention) versus the occurrence of wound complications (wound drainage, breakdown, necrosis, dehiscence, superficial or deep infection) requiring additional intervention. Intervention will be defined as any attempt of the surgeon to improve wound healing (in-office debridement, topical ointment, aspiration, antibiotic therapy, or return to the OR for the wound). Secondary outcome measures will include duration of wound healing delay, length of hospital stay, number of days of antibiotic therapy, and direct and estimated indirect costs. Statistical analysis will be performed to detect differences in the treatment groups

An *a priori* sample size calculation was performed based on data from our pilot study and from the existing literature. Currently, our retrospective data indicates wound complications should occur in approximately 31% of our "high risk" patients in the control group. We do not have reliable retrospective data for the study ciNPT group, so we are assuming a 4.57 relative risk reduction in wound complications using the ciNPT device based on existing data in the literature. An intention-to-treat analysis will be used. Given the short-term nature of this study, our expected dropout rate is very close to zero (and will in all likelihood be zero). Assuming an ITT analysis, any dropouts should be counted as failures. With an estimated dropout rate of 5%, the incidence of wound complications in the control group would be 34.5% and the incidence of wound complications in the ciNPT group would be 11.5%. Our assumptions include an equality analysis, 2-sided p-value < 0.05, and Fisher's exact test. Using these baseline assumptions, 116 patients (58 per group) will be required to achieve 80% power.

Based on our pilot study, 37% of our patient population should meet our inclusion criteria. Patients will need to be followed for at least 90 days to assess postoperative wound healing complications.

INCLUSION AND EXCLUSION CRITERIA Subject Selection

Version Date: 10/22/12 Page 3 of 6

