Prospective inclusion criteria:

- 1. Patients undergoing primary THA through a direct anterior approach by one of the investigating surgeons
- 2. The presence of one or more of these risk factors for delayed or problematic wound healing:
 - a. Diabetes
 - b. Obesity (BMI > 30)
 - c. Active smoking
 - d. Previous Hip Surgery

RECRUITMENT PROCEDURES

Patients will be recruited in the offices of the treating surgeon if they meet subject criteria, based on routine consultation. No active recruitment, such as advertisements, will be made. No compensation will be offered to participants.

DATA COLLECTION

Columbia University Medical Center will be used as a central location for data processing and management. Vanderbilt University, with collaboration from a consortium of institutional partners, has developed a software toolset and workflow methodology for electronic collection and management of research and clinical trial data. REDCap (Research Electronic Data Capture) data collection projects rely on a thorough study-specific data dictionary defined in an iterative self-documenting process by all members of the research team with planning assistance from the Biostatistics Unit of Columbia University Medical Center. The iterative development and testing process results in a well-planned data collection strategy for individual studies. REDCap servers are housed in a local data center at Columbia and all web-based information transmission is encrypted. REDCap has been disseminated for use locally at other institutions and currently supports 965 active institutional partners and other institutions in 78 countries (www.project-redcap.org).

INFORMED CONSENT

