Patients willing to participate in the prospective study will be given written informed consent preoperatively. This will be performed by one of the investigators. Subjects will be informed that this study is being done to evaluate the potential effects of closed incision negative pressure therapy (ciNPT) on reduction of overall wound complications following direct anterior approach (DAA) total hip arthroplasty (THA) in high-risk patients compared to the standard dry dressing. Participating allows the researcher to use data from his/her medical record. No identifying information will be transmitted to other parties. Benefits and risks of participation will also be explained. Patients will also be given the option not to participate and receive routine care. Tests and treatment given will be a part of the standard of care and no extra procedures or treatments will be required for solely research purpose.

DISCOMFORTS AND RISKS

The Prevena Incision Dressing has an acrylic adhesive coating and a skin interface layer with silver, which may present a risk of an adverse reaction (redness, rash, itching, swelling or bruising) in patients who are allergic or hypersensitive to acrylic adhesives or silver. These risks are essentially identical to those seen with the control dressing. Please note that there is no evidence to support the risk of adverse skin reaction will be any higher than that of a traditional postoperative dressing. No additional risks to the standard care are anticipated for this study.

POTENTIAL BENEFITS

This includes improved wound healing from the use of the negative pressure dressing. The goal of this study is to determine if there is advantage of using this dressing on a routine basis compared to the standard dressing.

DEVICE PRECAUTIONS

Participants should contact the investigator in the event of visual or audible alerts as this may signal a leak, full canister, low battery, or device error. Participants need to remove the Prevena device prior to having a magnetic resonance imaging procedure or other diagnostic imaging procedures. The device should not be worn during hyperbaric oxygen therapy. Contact with the device must be avoided in the event of defibrillation or electrocardiograms.

DISCONTINUATION OF STUDY/SUBJECT WITHDRAWAL

Version Date: 10/22/12 Page 4 of 6

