If subject wish to be withdrawn from the study at anytime, then they may do so and contact the surgeon investigators with this request. Subjects may also be withdrawn by the investigators for the follow reasons:

- failure to follow instructions,
- failure to show up for study visits,
- it is not in the subject's best interest to continue on this study, or
- the study is stopped.

ADVERSE EVENTS

Adverse events occurring as a result of experimental intervention is not anticipated. However, if such event does arise, this will be documented and written report will be given to the IRB and sponsor.

DATA AND SAFETY MONITORING

The Principal Investigator will be tasked with ensuring the safety of the study. The Principal Investigator will review the aggregate data every 6 months to determine if aspects of the study need to be changed or stopped. In addition, the Principal Investigator will review any and all deviations, adverse events and unanticipated problems that may occur to determine their relatedness to the study, their severity, and whether they require study changes. In addition, any unanticipated problems or instances of non-compliance will be reported to the IRB as per their reporting requirements. If any protocol changes are needed, the investigator will submit a modification request to the IRB. Protocol changes will not be implemented prior to IRB approval unless necessary to eliminate apparent immediate hazards to the research subjects. In such a case, the IRB will be promptly informed of the change following implementation.

CRITERIA FOR EVALUATING RESPONSE/STATISTICAL ANALYSIS

For the randomized control trial, a t-test for independent samples or a nonparametric Mann-Whitney U test will be used for determination of differences of mean values between the two treatment groups. The Kolmogorov-Smirnov test will determine the distribution form. For analysis of categorical data, a Fisher exact test will be used. The level of alpha will be set at p < 0.05.

REFERENCES/BIBIOGRAPHY

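### The plan gives two different scopes for adverse events and no outcome for dressing skin reactions, so a between-arm comparison of that harm would be incomplete and open to ascertainment bias

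*Combined protocol and SAP*

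**What the plan says.** **Documentation.** The Adverse Events section states: "Adverse events occurring as a result of experimental intervention is not anticipated. However, if such event does arise, this will be documented". A written report then goes to the IRB and the sponsor. This is the plan's only explicit commitment to document adverse events.

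**Review.** The Data and Safety Monitoring section, directly after it, says that "the Principal Investigator will review any and all deviations, adverse events and unanticipated problems that may occur to determine their relatedness to the study", together with their severity and whether the study needs changing. It is not limited to one arm.

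**The named harm.** Discomforts and Risks says that the adhesive and silver layer of the ciNPT dressing "may present a risk of an adverse reaction (redness, rash, itching, swelling or bruising" in allergic or hypersensitive patients. It adds: "These risks are essentially identical to those seen with the control dressing".

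**Outcomes.** Under Experimental Design, the primary outcome concerns "wound complications (wound drainage, breakdown, necrosis, dehiscence, superficial or deep infection) requiring additional intervention". The secondary list reads "Secondary outcome measures will include duration of wound healing delay, length of hospital stay, number of days of antibiotic therapy", followed by costs. Skin reaction is in neither list. The statistical analysis section chooses tests by type of data and plans no safety comparison.

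**Setting.** Neither patients nor treating surgeons are blinded. Both dressings come off at 7 days; the control dressing is removed at home by the patient or a visiting nurse. Wounds in both arms are assessed and photographed at 2 and 6 weeks.

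**The concern.** A rash under the control dressing cannot be a result of the experimental intervention. Under the Adverse Events sentence alone, a reaction under ciNPT would be documented and the same reaction under the control dressing would not. The monitoring section points the other way, since relatedness can be judged only once an event has been noted. Staff following one section would collect different data from staff following the other.

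What is at stake is the safety side of the trial's own question, namely whether routine use of ciNPT has an advantage over the standard dressing. That calls for harms counted alike in both arms. The plan asserts that the skin risk is the same with both dressings but does not set up data collection that could support or contradict the assertion.

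**Working it through.** **1. The plan's own figure.** The inputs under Experimental Design are a 31% control complication rate, a 4.57-fold reduction, 5% dropout counted as failure, a two-sided 0.05 level and Fisher's exact test.
- ciNPT rate: 31% / 4.57 = 6.8%.
- With dropouts as failures: 0.31 × 0.95 + 0.05 = 34.45%, and 0.0678 × 0.95 + 0.05 = 11.44%. The plan states 34.5% and 11.5%.
- Exact Fisher power, summing over both binomial distributions at 34.5% vs 11.5%: 79.5% with 57 per arm and 80.5% with 58.

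The stated 58 per arm reproduces and is used below.

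**2. The two scopes side by side.**

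| Section | Which events | When relatedness is judged |
|---|---|---|
| Adverse Events | those resulting from the experimental intervention | before documentation |
| Data and Safety Monitoring | all | after the event is noted |

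Neither section gives a collection window, a scheduled question or a procedure common to both arms.

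**3. What unequal recording could do.** This is an illustration: the reaction rate and the recording fractions are assumptions, and the plan names no such test. Let the true rate be p = 10% in both arms, with every ciNPT reaction recorded and a fraction c of control reactions recorded. Recorded counts are then Binomial(58, 0.10) on ciNPT and Binomial(58, 0.10c) on control. The last column is the probability that two-sided Fisher gives p < 0.05 with the excess on ciNPT.

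| c | Expected recorded, ciNPT vs control | False significant excess on ciNPT |
|---|---|---|
| 100% | 5.8 vs 5.8 | 1% |
| 50% | 5.8 vs 2.9 | 8% |
| 25% | 5.8 vs 1.45 | 22% |
| 0% | 5.8 vs 0 | 53% |

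The last row can be checked by hand. Against 0/58, Fisher gives p = 0.057 for 5 events and p = 0.027 for 6, so significance needs at least 6, and P(X ≥ 6) with n = 58 and p = 0.10 is 0.529. With c = 0, the figure is 7% at an assumed rate of 5% and 88% at 15%. By symmetry, if ciNPT were the arm with half its reactions recorded and control were complete, the same 8% would be a false excess on control.

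**4. What 58 per arm could show with equal recording.** Exact Fisher power is 8% for 5% vs 10%, 31% for 5% vs 15%, 61% for 5% vs 20% and 83% for 5% vs 25%. With 0/58 events, the one-sided 95% upper limit is 1 − 0.05^(1/58) = 5.0%. This sample supports estimation with an interval better than a test.

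**The case against.** The strongest reply is that the monitoring section already covers all adverse events in both arms, and that the Adverse Events sentence is mainly a reporting rule for the IRB and sponsor. In addition, wounds in both arms are examined and photographed at 2 and 6 weeks, medical-record data may be used, and the study's data dictionary is not among the documents. Part of this stands. A reader might infer that control reactions will go unrecorded, or that the harm cannot be compared at all. The documents do not support either inference. But the monitoring text governs review, and it sets no common collection procedure. The first stated wound assessment comes a week after dressing removal, when a transient reaction may have cleared, and a photograph does not show itching.

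A reader might also take the 53% as the expected bias, or assume that the bias runs against ciNPT. The 53% needs an assumed 10% rate and no control recording at all. The direction is open: unblinded investigators who do not anticipate intervention-related events could under-record on ciNPT instead.

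Two further inferences go too far. One is that ointment for a rash would contaminate the primary outcome. That outcome requires a listed complication as well as an intervention, and "Intervention will be defined as any attempt of the surgeon to improve wound healing (in-office debridement, topical ointment, aspiration, antibiotic therapy" ties the intervention to wound healing. Ointment given only for a rash away from the incision meets neither condition. The other is that hypersensitive patients would necessarily be randomised. The criteria list no exclusion, but surgeons recruit through routine consultation and investigators may withdraw a subject in that subject's interest.

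Finally, the sample is too small to settle whether the risks are identical, however well they are recorded. That is true, and it is a reason to report estimates, not to leave collection uneven.

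**Conclusion.** The point holds as a cheap improvement. The Adverse Events and Data and Safety Monitoring sections give different scopes and must be reconciled. No outcome captures the skin reactions that the protocol itself names. In this unblinded trial a comparison of them would be incomplete and open to ascertainment bias of uncertain direction. How large that bias could be depends on assumptions the documents cannot settle: at a 10% rate with full ciNPT recording, the chance of a false significant excess on ciNPT runs from 1% with equal recording to 53% with no control recording. The sample size and primary analysis are unaffected.

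**What to change.** 1. Keep the sentence on reporting to the IRB and sponsor, and state next to it that adverse events are recorded in both arms regardless of attribution. This brings the section into line with Data and Safety Monitoring.
2. At the existing 2-week visit, add one yes/no field, identical in both arms: redness, rash, itching, swelling or bruising under the dressing, present now or noticed at or since dressing removal. The second half of the question covers reactions that cleared after day 7.
3. List this as a safety outcome and report counts by arm with confidence intervals, without a significance test.
4. Reconcile the eligibility section, which lists only inclusion criteria such as "The presence of one or more of these risk factors for delayed or problematic wound healing", with the hypersensitivity hazard in Discomforts and Risks.

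The cost is one field and one table, with no extra visit. The drawbacks are some reliance on patient recall and a possibly non-zero reported reaction rate on ciNPT.

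### Mann-Whitney is described as a comparison of means, so skewed costs could be left with no test of mean cost, only a rank test reported as one (minor)

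*Combined protocol and SAP*

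**What the plan says.** The section on criteria for evaluating response and statistical analysis states that an independent-samples t-test or a "nonparametric Mann-Whitney U test will be used for determination of differences of mean values between the two treatment groups". It adds: "The Kolmogorov-Smirnov test will determine the distribution form". The natural reading is that this result selects between the two tests, but that is not written, and neither the version of the test nor its significance level is given. Categorical data go to Fisher's exact test.

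The secondary outcomes under Experimental Design are healing delay, length of stay, "number of days of antibiotic therapy, and direct and estimated indirect costs". No other analysis of costs appears anywhere, and no device price, complication cost or cost SD is given.

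**The concern.** The sentence assigns the same target, a difference in means, to two tests. Only the t-test has that target. Mann-Whitney asks whether a patient in one arm tends to rank above a patient in the other.

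Costs are where this can matter. A device premium, if there is one, falls on every ciNPT patient. Complication costs fall on a minority and are uneven, because an intervention can be any of "in-office debridement, topical ointment, aspiration, antibiotic therapy, or return to the OR for the wound". Ranks follow the frequent small premium, while the mean follows the rare large cost. A budget holder needs the mean and, given the plan's wording, would take the p-value to be about the mean.

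For length of stay, antibiotic days and healing delay there is no per-patient device cost pulling against the benefit, so only the label is wrong.

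**Working it through.** **Inputs from Experimental Design.** Control complication rate 31%; an assumed reduction given as 4.57; 5% dropout counted as failures; 34.5% versus 11.5% after dropout; 58 per arm; two-sided 0.05.

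**Plan's own figures.** Reading 4.57 as a rate ratio gives 0.31/4.57 = 0.0678, or 6.8%. With dropouts as failures, 0.31 × 0.95 + 0.05 = 0.3445 and 0.068 × 0.95 + 0.05 = 0.1146, which match 34.5% and 11.5%. Exact Fisher power at 58 per arm is 80.5% (79.5% at 57), so 116 patients is reproduced. For costs, 31% versus 6.8% is the better pair, since a dropout counted as a failure need not incur a complication cost.

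**Where the mean changes sign.** Let D be the ciNPT premium over the control dressing and K the mean cost of a complication. Neither is in the documents.

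Mean difference (ciNPT − control) = D − K(0.31 − 0.0678) = D − 0.2422K.

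Break-even: K/D = 1/0.2422 = 4.13 (at 34.5% versus 11.5% it is 1/0.23 = 4.35). At K = 10D the true saving is 2.42D − D = 1.42D.

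**Where the ranks point.** Suppose other costs and complication costs are nearly constant and K exceeds D. A ciNPT patient then costs more than any uncomplicated control, and more than a complicated control only if also complicated:

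P(ciNPT dearer) = 0.69 + 0.31 × 0.0678 = 0.71 (0.655 + 0.345 × 0.115 = 0.69 on the other pair).

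This does not depend on K, so above 4.13D the ranks and the mean disagree. Variation in other costs weakens the effect.

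**Simulation.** 58 per arm and 20,000 trials per cell, with normal other costs and gamma complication costs. K-S uses fitted mean and SD at 5%. Mann-Whitney is used if either arm is flagged, otherwise Student's t. CV is that of complication cost. Results in % at K = 10D:

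| SD of other costs | 0.25D | 1D | 2D | 4D | 8D |
|---|---|---|---|---|---|
| ciNPT called dearer, CV 0.5 | 94 | 16 | 1 | 0 | 0 |
| ciNPT called dearer, CV 1 | 98 | 30 | 3 | 1 | 0 |
| ciNPT called dearer, CV 2 | 100 | 78 | 18 | 4 | 1 |
| Saving found, CV 0.5 | 0 | 0 | 11 | 24 | 13 |
| Same, Welch | 42 | 40 | 36 | 25 | 13 |
| Saving found, CV 2 | 0 | 0 | 0 | 2 | 5 |
| Same, Welch | 5 | 5 | 6 | 6 | 7 |

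At CV 0.5, K-S flags 100/100/88/6/0% of trials across these SDs, so Mann-Whitney is what would be used in the cells where reversal occurs.

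**No premium** (complication cost 10 units, SD 0.25 to 8 units). ciNPT is called dearer in at most 0.2% of trials. At CV 0.5 the saving is found in 62/62/61/59/30% against Welch's 87/86/80/60/30%.

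**Dependence on the unstated K-S rule** (K = 10D, CV 0.5). With the Lilliefors correction at SD 4D, 68% of trials are flagged instead of 6%, and the saving is found in 17% instead of 24%. If Mann-Whitney is used only when both arms are flagged, the saving at SD 2D is found in about 28% instead of 11%. Reversal at SD 0.25D and 1D hardly changes (94% and 15%).

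**The case against.** **The t-test is named in the same sentence.** A reader might infer that the plan offers costs no test of means at all. That is too strong: if normality is not rejected, means are compared. The gap opens only when costs are skewed enough to be flagged.

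**Every cost input is assumed.** A reader might infer that the cost result will point the wrong way. The documents do not support that. Reversal needs a premium, K above 4.13D and little variation in other costs, and nothing in the documents establishes any of the three. At SD 4D it is 0 to 1% for CV 0.5 and 1, and 4% for CV 2. This objection stands, and it is why the size is only a scenario.

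**Direct and indirect costs may be two outcomes.** The premium belongs to direct cost. If indirect cost is analysed separately, reversal does not arise there, although some power may still be lost. This also stands.

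**The power gain may be small.** The Introduction reports 11.5% wound complications and 1.9% reoperations, so about five in six complications (1 − 1.9/11.5 = 0.83) did not lead to reoperation. That suggests heavy-tailed costs, nearer CV 2, where Welch finds the saving in only 5 to 7% of trials. The case for the change therefore rests on testing the stated target, not on power.

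**Cost items and missing costs.** A reader might add that no cost items are listed and that counting dropouts as failures assigns no cost. These are missing details rather than errors, and the plan expects dropout close to zero.

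**Conclusion.** Wrong as written, and minor. It is certain from the text that Mann-Whitney is given a target it does not have, and that costs have only the generic pair of tests. Skewed costs could therefore be tested on ranks and reported as means.

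The consequence depends on prices the documents do not give. With a premium D, K above about 4.13D and other-cost SD of about D or less (about 2D with heavy tails), the result can be significant in the wrong direction. Above break-even but with wider variation, or with no premium, reversal is rare. The loss is then one of power, by an amount that turns on the unstated K-S rule, and at large SD it is nil or nearly so.

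Costs are one of several secondary outcomes. The null hypotheses concern complications and reoperation and do not mention costs. Nothing here touches the primary outcome, the Fisher test or the 116 patients.

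**What to change.** For costs, remove the normality pretest. Pre-specify the difference in arithmetic mean cost between the randomised arms, with a Welch or bootstrap 95% confidence interval. If direct and indirect costs are separate outcomes, do this for each. Where Mann-Whitney is kept for length of stay, antibiotic days and healing delay, describe it as a rank comparison and remove the reference to mean values.

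This takes two or three sentences and needs no new data and no change in sample size. There are downsides:

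- The interval may be wide. The mean Welch half-width runs from 1.6D to 4.4D, against a saving of 1.42D at K = 10D.
- With very heavy-tailed complication costs (CV 2), Welch coverage is 89/89/90/92/95% at SD 0.25D/1D/2D/4D/8D.
- Near break-even with such tails (K = 5D, CV 2), Welch also errs in direction, in 7.0% and 5.4% of trials at SD 0.25D and 1D. The pretest rule does so in 100% and 86%.

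These figures are for Welch; the bootstrap interval was not simulated.
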